## 1.4 Rationale for the Study

While influenza affects all age groups, infants and young children remain at increased risk for influenza because of their maturing immune system and lack of prior exposure and thus lack of immunity. Therefore, following a similar rationale that has been applied for adults 65 years of age and older, children may benefit from an increased antigen dose. Thus, this Phase II study will evaluate if an increased antigen dose in the QIV-HD investigational product is safe and will improve immune responses in the pediatric population aged 6 months to 17 years compared to currently licensed standard-dose quadrivalent influenza vaccines (QIV-SD) (15 µg HA/strain). The goal of QHD04 is to select the appropriate vaccine dosage for advancement to Phase III clinical development.

QHD04 is planned to be conducted during the 2018-2019 NH influenza season in approximately 700 children 6 months to 17 years of age and will evaluate 3 different dosages of QIV-HD in this pediatric population. The comparator vaccine will be Fluarix Quadrivalent which is a unadjuvanted QIV-SD and is manufactured by GlaxoSmithKline (GSK). Furthermore, another comparator vaccine, FLUAD Pediatric, which is an adjuvanted TIV and manufactured by Seqirus, will also be evaluated since FLUAD Pediatric is the only licensed pediatric vaccine which has been evaluated in relative efficacy studies. FLUAD Pediatric is only licensed for the pediatric indication (6 months to < 2 years of age) in Canada.

## 2 Study Objectives

### *Safety*

To describe the safety of each dosage of QIV-HD used in the study during the 28 days following each vaccination, and serious adverse events (SAEs) (including adverse events of special interest [AESIs]) throughout the study.

The endpoints for the safety objective are presented in [Section 9.1.2](#)

### *Immunogenicity*

- To describe the antibody response induced by each dosage of QIV-HD used in the study compared with unadjuvanted QIV-SD by hemagglutination inhibition (HAI) measurement method.
- To describe the antibody response induced by each dosage of QIV-HD used in the study compared with unadjuvanted QIV-SD by virus seroneutralization (SN) measurement method.

- To describe the antibody response induced by the highest acceptable dosage of QIV-HD compared with adjuvanted TIV by HAI and virus SN measurement methods.

The endpoints for the immunogenicity objective are presented in [Section 9.2.1](#)

### 3 Investigators and Study Organization

This study will be conducted in 16 centers in the US and Canada. The Principal Investigators and any sub-investigators at the individual sites will be coordinated by 1 Coordinating Investigator. Details of the study centers, the Investigators at each center, and the Coordinating Investigator are provided in the “List of Investigators and Centers Involved in the Trial” document.

#### ***Safety Management Team***

An internal safety management team (SMT) will perform an analysis of safety data during the conduct of the study after the first vaccination (Early Safety Data Review [ESDR]).

#### ***Monitoring, Data Management, and Statistical Analysis***

Biostatistics, data management, monitoring, and medical writing will either be subcontracted to a Contract Research Organization (CRO) or performed in-house by the Sponsor.

#### ***Laboratory Analysis***

Testing will be performed at Sanofi Pasteur’s Global Clinical Immunology (GCI) department or at an outsourced laboratory under the supervision of GCI.

The Sponsor’s Responsible Medical Officer (the RMO, the person authorized to sign this protocol and any amendments on behalf of the Sponsor) is [REDACTED] Clinical Team Leader (CTL).

### 4 Independent Ethics Committee / Institutional Review Board

Before the investigational product can be shipped to the investigational site and before the inclusion of the first subject, this protocol, the informed consent form (ICF), the assent form, subject recruitment procedures, and any other written information to be provided to subjects must be approved by, and / or receive favorable opinion from, the appropriate Independent Ethics Committees (IECs) or Institutional Review Boards (IRBs).

In accordance with Good Clinical Practice (GCP) and local regulations, each Investigator and / or the Sponsor are responsible for obtaining this approval and / or favorable opinion before the start of the study. If the protocol is subsequently amended, approval must be re-obtained for each substantial amendment. Copies of these approvals, along with information on the type, version number, and date of document, and the date of approval, must be forwarded by the Investigator to the Sponsor together with the composition of the IEC / IRB (the names and qualifications of the members attending and voting at the meetings).

The Investigator or Sponsor will submit written summaries of the status of the study to the IEC / IRB annually, or more frequently if requested. All SAEs occurring during the study that are

related to the product administered will be reported to the IEC / IRB, according to the IEC / IRB policy.

## 5 Investigational Plan

### 5.1 Description of the Overall Study Design and Plan

#### 5.1.1 Study Design

QHD04 will be a Phase II, randomized, staged, modified double-blind, active-controlled, multi-center study to be conducted in 700 children 6 months 17 years of age to evaluate the safety and immunogenicity of 3 dosages of QIV-HD administered by IM route versus QIV-SD or adjuvanted TIV.

The study will be divided into 13 groups and will enroll in 4 stages. The study will use a stepwise age de-escalation and dose ascension design for children 6 months to < 5 years of age.

Children 5 to 8 years of age will also undergo a dose ascension design and begin enrollment in Stage 1. Children 9 to 17 years of age will be enrolled in Stage 1 and randomized to receive all three dose formulations (ie, 30 µg, 45 µg, and 60 µg HA/strain/dose). An ESDR will be conducted after Visit (V) 02 (at Day [D] 8 post-vaccination) of Stages 1, 2, and 3 for children 6 months to < 5 years of age and Stages 1 and 2 for children 5 to 8 years of age. The ESDR for children 6 months to < 5 years of age will be independent of the ESDR for children 5 to 8 years of age. Enrollment of subjects in the next stage will be initiated if the safety review results are satisfactory.

The 13 study groups are divided according to:

- Age (9 to 17 yearsa, 5 to 8 yearsb, 36 months to < 5 years, 6 to < 36 months, or 6 to < 24 months)
- Influenza vaccination history (previously influenza vaccinated, previously influenza unvaccinated, or both)
- Administered vaccines (QIV-HD dosages [30 µg, 45 µg, or 60 µg HA/strain/dose], unadjuvanted QIV-SD, and adjuvanted TIV).

The study design and the safety reviews are described in [Table 5.1](#) and [Section 5.1.6](#), respectively. The study flow chart is outlined in [Figure 5.1](#), [Figure 5.2](#), and [Figure 5.3](#). The details of the study design are described below.

Stage 1 will include 3 age groups (36 months to < 5 years, 5 to 8 years, and 9 to 17 years) and will be conducted in the US:

a “9 to 17 years” means from the 9th birthday to the day before the 18th birthday.

b “5 to 8 years” means from the 5th birthday to the day before the 9th birthday.

- Previously influenza vaccinated and unvaccinated subjects 36 months to < 5 years of age (Group 1) will be randomized to receive either QIV-HD at 30 µg HA/strain/dose or the unadjuvanted QIV-SD. Based on the early safety data review, the study will either stop (Group 1 does not pass safety review) or continue into Stage 2 .
- Previously influenza vaccinated and unvaccinated subjects 5 to 8 years of age (Group 9), will be randomized to receive either QIV-HD at 30 µg HA/strain/dose or the unadjuvanted QIV-SD. Based on the early safety data review, the enrollment of this age group will either stop (Group 9 does not pass safety review) or continue into Stage 2.
- Previously influenza vaccinated and unvaccinated subjects 9 to 17 years of age (hereafter will be referred to as subjects 9 to 17 years of age) will be divided into 2 groups (Group 12 and Group 13). Group 12 will be enrolled first and will be randomized to receive either QIV-HD at 30 µg, or 45 µg HA/strain/dose or the unadjuvanted QIV-SD. Once the enrollment of Group 12 is complete, subjects in Group 13 will be randomized to receive either QIV-HD at 60 µg or the unadjuvanted QIV-SD. Subjects 9 to 17 years of age will not undergo an ESDR.

Stage 2 will include 3 age groups (6 to < 36 months, 36 months to < 5 years, and 5 to 8 years) and will be conducted in the US:

- Previously influenza vaccinated and unvaccinated subjects 36 months to < 5 years of age (Group 2) will receive either QIV-HD at 45 µg HA/strain/dose or the unadjuvanted QIV-SD and previously influenza vaccinated and unvaccinated subjects 6 to < 36 months of age (Group 3) will receive either QIV-HD at 30 µg HA/strain/dose or the unadjuvanted QIV-SD. Based on the early safety data review, the study will either stop (Group 3 does not pass safety review), continue and skip to Stage 4 (Group 2 does not pass safety review), or continue to Stage 3 (Group 2 and Group 3 both pass the safety review).
- Previously influenza vaccinated and unvaccinated subjects 5 to 8 years of age (Group 10), will be randomized to receive either QIV-HD at 45 µg HA/strain/dose or the unadjuvanted QIV-SD. Based on the early safety data review, the enrollment of this age group will either stop (Group 10 does not pass safety review) or continue into Stage 3.

Stage 3 will include 3 age groups (6 to < 36 months, 36 months to < 5 years, and 5 to 8 years) and will be conducted in the US:

- Previously influenza vaccinated and unvaccinated subjects 36 months to < 5 years of age (Group 4) will receive either QIV-HD at 60 µg HA/strain/dose or the unadjuvanted QIV-SD; and previously influenza vaccinated and unvaccinated subjects 6 to < 36 months of age (Group 5) will receive either QIV-HD at 45 µg HA/strain/dose or the unadjuvanted QIV-SD. Based on the early safety data review, the highest dosage with an acceptable safety review will be determined and used in Stage 4.
- Previously influenza vaccinated and unvaccinated subjects 5 to 8 years of age (Group 11) will be randomized to receive either QIV-HD at 60 µg HA/strain/dose or the unadjuvanted QIV-SD.

Stage 4 will include 2 age groups (6 to < 36 months and 6 to < 24 months) and will be conducted in the US (subjects 6 to < 36 months) and Canada (subjects 6 to < 24 months):

- Previously influenza unvaccinated subjects 6 to < 36 months of age (Group 6) and previously influenza vaccinated subjects 6 to < 36 months of age (Group 7) will be randomized to receive either the highest dosage of QIV-HD with an acceptable safety review or the unadjuvanted QIV-SD.
- Previously influenza unvaccinated subjects 6 to < 24 months of age (Group 8) will receive either the highest dosage of QIV-HD with an acceptable safety review or the adjuvanted TIV.

**Table 5.1: Description of study design**

Stage (Country)	Age Group (Vaccination Status*)	Study Group	N	Vaccine	Vaccine Dosage ( $\mu$ g HA/strain/dose) †
1 (US)	9 to 17 years (previously vaccinated and unvaccinated)	12	30	QIV-HD	30
			30	QIV-HD	45
			10	unadjuvanted QIV-SD	15
	9 to 17 years (previously vaccinated and unvaccinated)	13	30	QIV-HD	60
			30	unadjuvanted QIV-SD	15
	5 to 8 years (previously vaccinated and unvaccinated)	9	30	QIV-HD	30
			10	unadjuvanted QIV-SD	15
	36 months to < 5 years (previously vaccinated and unvaccinated)	1	30	QIV-HD	30
			10	unadjuvanted QIV-SD	15
2 (US)	5 to 8 years (previously vaccinated and unvaccinated)	10	30	QIV-HD	45
			10	unadjuvanted QIV-SD	15
	36 months to < 5 years (previously vaccinated and unvaccinated)	2	30	QIV-HD	45
			10	unadjuvanted QIV-SD	15
	6 to < 36 months (previously vaccinated and unvaccinated)	3	30	QIV-HD	30
			10	unadjuvanted QIV-SD	15
3	5 to 8 years	11	30	QIV-HD	60

Stage (Country)	Age Group (Vaccination Status*)	Study Group	N	Vaccine	Vaccine Dosage ( $\mu$ g HA/strain/dose)†
(US)	(previously vaccinated and unvaccinated)		30	unadjuvanted QIV-SD	15
	36 months to < 5 years (previously vaccinated and unvaccinated)		45	QIV-HD	60
	4	45	unadjuvanted QIV-SD	15	
	6 to < 36 months (previously vaccinated and unvaccinated)	5	30	QIV-HD	45
			10	unadjuvanted QIV-SD	15
4 (US)	6 to < 36 months (previously unvaccinated)	6	30	QIV-HD	30, 45, or 60†
			30	unadjuvanted QIV-SD	15
	6 to < 36 months (previously vaccinated)	7	30	QIV-HD	30, 45, or 60†
			30	unadjuvanted QIV-SD	15
4 (Canada)	6 to < 24 months (previously unvaccinated)	8	30	QIV-HD	30, 45, or 60†
			30	adjuvanted TIV	7.5

Abbreviations: HA, hemagglutinin; QIV-SD, standard-dose quadrivalent influenza vaccine; TIV, trivalent influenza vaccine;  $\mu$ g, microgram.

\* Vaccination status is determined by information provided by the parent / guardian.

† Dosage selection will be based on the ESDR of the prior Stages. The highest dosage with an acceptable safety review from prior Stages will determine the dose evaluated in Stage 4.

Figure 5.1: Study design flow chart for subjects 6 months to < 5 years of age

[figure not shown]

Figure 5.2: Study design flow chart for subjects 5 to 8 years of age

[figure not shown]
[figure not shown]

Figure 5.3: Study design flow chart for subjects 9 to 17 years of age

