#### ***Review of safety data***

The study will be divided into 4 stages as described in [Section 5.1.1](#). An ESDR will be conducted for subjects 6 months to 8 years of age. The ESDR will occur following the collection of the safety data at V02 (approximately 8 days post-vaccination) of Stages 1, 2, and 3 by the SMT. Enrollment of subjects in the next stage will be initiated if the safety review results are satisfactory. The details of the safety reviews are described in [Section 5.1.6](#).

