***Visit 2 (8 [+3] days after Visit 1): Collection of Safety Information – for subjects 6 months to 8 years of age***

**Note:** If Visit 2 falls on a weekend or a holiday, the visit may be scheduled on the next business day.

The Investigator or delegate will:

- 1) Review (for clarity, content, and completeness) the information in the DC1 with the subject or subject's parent / guardian and clarify with the subject or subject's parent / guardian, if required, any AEs, medications (see [Section 6.7](#)), or SAE that occurred since V01. If an SAE occurred, follow the instructions in [Section 10](#) for reporting it.
- 2) Record the D0 to D7 safety data in the CRB.
- 3) Remind the subject or subject's parent / guardian to do the following:
  - Complete the remaining pages of the DC1 and bring the completed diary to V03
  - Notify the site in case of an SAE.

***Visit 3 (28 [+7] days after Visit 1) – for subjects 9 to 17 years of age and for previously influenza vaccinated subjects 6 months to 8 years of age***

Note: Subjects 9 to 17 years of age are scheduled for 2 site visits. However, the second visit is designated as V03 to be consistent with the visit nomenclature of the 6 months to 8 years age groups.

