### 5.1.6 Early Safety Data Review

The safety of the investigational product will be continuously monitored by the Sponsor. ESDRs will be performed, the goal of which is to allow for a cautious, stepwise approach to vaccine administration. A stepwise dosage ascension approach will be applied to subjects in age group 5 to 8 years (30 µg, 45 µg, and 60 µg HA/strain/dose). A stepwise age de-escalation vaccination approach will be taken for subjects in age group 36 months to < 5 years of age, with an ESDR prior to vaccinating subjects in the age group 6 to < 36 months of age as well as stepwise dosage ascension. The ESDR will be performed following V02 in subjects 6 months to 8 years of age (refer to [Figure 5.1](#) and [Figure 5.2](#)).

The ESDRs for this study are planned after the 6 months to 8 years age groups in each stage have been vaccinated and have provided safety data for Days 0 to 7 post-vaccination, using the data collection methods described in the protocol. ESDR will not be performed for subjects 9 to 17 years of age.

---

a Enrollment of subjects 9 to 17 years of age may be extended

During each ESDR, enrollment of subjects will be paused. However, already enrolled subjects 6 months to 8 years of age who require 2 vaccinations because of their previous vaccination status will receive their second dose at D28 as scheduled, which may be prior to the ESDR. Following a satisfactory safety review, enrollment of subjects will resume for the subsequent or appropriate Stage as described in [Figure 5.1](#) and [Figure 5.2](#). The study visits according to the [Table of Study Procedures](#) will continue to be followed for enrolled subjects within each active Stage (ie, subjects will complete their scheduled visits).

The safety data collected will be entered into the CRBs and summarized by the Sponsor in a blinded manner. A review will be performed by the Sponsor during the SMT meetings. It is understood that this review is based on preliminary data that have not been subject to validation and database lock. (The usual and ongoing process of monitoring safety signals outside of those specified in the protocol-defined early interim safety analysis will continue unchanged.)

The following safety parameters will be assessed as part of the early safety review:

- Immediate reactions
- Solicited injection site and systemic reactions
- Unsolicited AEs
- SAEs (including AESIs)

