Enrollment will be paused during the review, and the data will be examined for the following occurrences:

- An SAE (including AESIs) considered as related to the vaccination by the Investigator and Sponsor
- > 10% of subjects experiencing Grade 3 fever within 7 days after vaccination

If any of the above criteria are met, a decision will be made as to whether enrollment in the study will be allowed to resume.

Case unblinding may be performed if necessary.

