## 12.4 Interim / Preliminary Analysis

For Stages 1, 2, and 3, there will be an early blinded look at the 7-day safety data for subjects 6 months to 8 years of age to determine whether the next group will be enrolled. No statistical adjustment is necessary because no hypotheses will be tested.

A limited statistical analysis of the unblinded safety and immunogenicity data obtained up to D28 or D56 may be conducted once data are available and an interim database lock has been conducted. A final analysis will be conducted once the 6-month safety data have been collected and the final database lock has occurred.

No statistical adjustment is necessary because no hypotheses will be tested.

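### If 60 µg is used in Stage 4, the plan's only numeric safety criterion is never applied to that dose in children under 36 months, because early safety reviews are specified for Stages 1 to 3 only

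*Protocol*

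**What the plan says.** The Stage 4 dose is chosen from earlier stages. The footnote to Protocol Table 5.1 reads "The highest dosage with an acceptable safety review from prior Stages will determine the dose evaluated in Stage 4". Section 5.1.1 says the same when it describes Stage 3: "the highest dosage with an acceptable safety review will be determined and used in Stage 4". Neither rule limits the choice to doses already reviewed in the same age group.

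The ESDR is tied to named stages:
- Protocol 5.1.1 places it after V02 "of Stages 1, 2, and 3 for children 6 months to < 5 years of age".
- Protocol 5.1.3, Review of safety data: "The ESDR will occur following the collection of the safety data at V02 (approximately 8 days post-vaccination) of Stages 1, 2, and 3".
- Protocol 12.4, repeated in SAP 5.4: "For Stages 1, 2, and 3, there will be an early blinded look at the 7-day safety data".

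Protocol 5.1.6 gives the purpose: "ESDRs will be performed, the goal of which is to allow for a cautious, stepwise approach to vaccine administration". It lists two criteria. One is any SAE judged related by both the Investigator and the Sponsor. The other, the only one with a rate, is "> 10% of subjects experiencing Grade 3 fever within 7 days after vaccination". Meeting either leads to a decision on whether enrollment resumes, not to an automatic stop.

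**The concern.** Children aged 6 to <36 months are reviewed at 30 µg (Group 3) and at 45 µg (Group 5), each time after 30 QIV-HD recipients. If 60 µg goes forward, the same age group gets no corresponding review of 60 µg. Below 5 years, the only earlier data on that dose come from Group 4, aged 36 months and over.

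Two features of the protocol make the fever check relevant in these children. Section 1.3.2 describes a fever-associated seizure risk at 6 months through 4 years that peaked at about 16 months, an age inside all three Stage 4 groups and outside Group 4. The same section says the excess was below 1 per 1000 and was not seen in 2012–2013. Also, 60 of the 90 children (Groups 6 and 8) are due a second dose at D28, and Grade 3 fever after dose 1 is not a listed contraindication in Section 5.2.7.2. A high fever rate after dose 1 would therefore prompt no planned decision.

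**Working it through.** **1. Plan totals.** Section 12.5: 6×40 + 90 + 60 + 2×60 + 2×60 + 70 = 700, which matches the stated total. No power figure exists to reproduce.

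**2. Exposure to 60 µg (Table 5.1).**

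| Group | Age | QIV-HD n | Stage | ESDR specified in 5.1.1 |
|---|---|---|---|---|
| 13 | 9–17 y | 30 | 1 | no |
| 11 | 5–8 y | 30 | 3 | no |
| 4 | 36 mo to <5 y | 45 | 3 | yes |
| 6, 7 | 6 to <36 mo | 30 + 30 | 4 | no |
| 8 | 6 to <24 mo | 30 | 4 | no |

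Under 36 months, the number given 60 µg in a stage with a specified ESDR is 0. The number in Stage 4, if 60 µg is chosen, is 30 + 30 + 30 = 90.

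**3. Fever scale.** Grade 3 is >39.5 °C below 36 months (Table 9.4) and ≥39.0 °C from 3 years (Table 9.5). The Group 4 review therefore applies the criterion on a different scale.

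**4. What a Stage 4 review would detect.** The documents give no fever rates. Assumed: 10%, 20% or 30% at 60 µg; 3% in controls (range 1% to 5%). The first 60 subjects at 1:1 are taken as 30 QIV-HD and 30 control, pooled because the review is blinded. More than 10% of 60 means at least 7. With X ~ Bin(30, p) and Y ~ Bin(30, c), the probability is P(X + Y ≥ 7):

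| 60 µg rate | c = 1% | c = 3% | c = 5% |
|---|---|---|---|
| 10% | 0.04 | 0.09 | 0.16 |
| 20% | 0.45 | 0.55 | 0.64 |
| 30% | 0.86 | 0.90 | 0.93 |

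At 5% versus 3%, a false trigger has probability 0.01. In Group 5's 30:10 mix the same criterion (at least 5 of 40, c = 3%) is met with probability 0.23, 0.78 and 0.98. The 1:1 allocation dilutes the signal.

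**5. How early it would report.** Section 5.1.5 plans Stage 4 inclusion from 03 January to 28 February 2019, 57 days inclusive. Assume even enrollment of all 180 subjects.
- 60th subject vaccinated: 57 × 60/180 = day 19.
- Lag: at least 11 days (D8 + 3). At most 24 days, the longest of the calendar's own gaps from last inclusion in one stage to the start of the next (17, 20 and 24 days).
- Review reports on day 30 to 43.
- First doses of QIV-HD given: 90 × 30/57 = 47 to 90 × 43/57 = 68. Open: 22 to 43.
- Second doses given: 60 × (30 − 28)/57 = 2 to 60 × (43 − 28)/57 = 16. Open: 44 to 58 of 60, including those of children not yet enrolled.

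**6. Upper bound on benefit.** If a met criterion always stopped 60 µg, dose-1 Grade 3 fevers avoided = open first doses × p × P(criterion met), with c = 3%:
- 10%: 22.1 × 0.10 × 0.091 = 0.2 to 42.6 × 0.10 × 0.091 = 0.4, of 9 expected.
- 20%: 22.1 × 0.20 × 0.549 = 2.4 to 42.6 × 0.20 × 0.549 = 4.7, of 18.
- 30%: 22.1 × 0.30 × 0.902 = 6.0 to 42.6 × 0.30 × 0.902 = 11.5, of 27.

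**The case against.** **Other oversight continues.** Section 5.1.6 keeps continuous Sponsor monitoring. Febrile convulsion is always an SAE (9.1.3.3), convulsions are an AESI (9.1.3.4), and SAEs are reported within 24 hours (10.1). Section 5.2.7.2 bars dose 2 after a related SAE and lets the Investigator withhold it for any condition posing a health risk. Sections 5.5 and 10.4 allow the study to be stopped or modified. All of this stands. A reader might infer that Stage 4 runs without safety oversight, and the documents do not support that. None of these provisions, however, contains a fever rate.

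**An ESDR opens the next stage, and Stage 4 has none.** This explains the omission, and Section 5.1.1 likewise lists no ESDR after the 60 µg step at 5 to 8 years. It does not change the fact that 60 µg is unreviewed in the youngest children.

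**Section 5.1.6 speaks of ESDRs in each stage.** Read alone, that could include Stage 4. The more specific statements name Stages 1 to 3, and the phrase sets no review point within Stage 4. Figure 5.1 was not available to check.

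**Group 4 clears a lower temperature threshold.** True, and mildly reassuring about the dose. It is evidence from older children only.

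**The benefit is small, and 20% to 30% implies a steep rise from 45 µg.** This largely stands. Group 5 would probably have met the criterion at such rates, so those scenarios assume a marked increase between 45 and 60 µg.

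**Conclusion.** The gap is real and conditional. If 60 µg is selected, up to 90 children under 36 months receive it without the plan's one numeric criterion being applied to that dose in their age group or on their fever scale. Closing it is a cheap improvement of modest value. The pooled check detects only large excesses, and roughly half to three quarters of first doses would be given before it reports; most second doses would still be open. The figures rest on assumed fever rates, one control rate across QIV-SD and adjuvanted TIV, and even enrollment. The benefit is an upper bound because a met criterion only prompts a decision.

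Two stronger readings do not hold. Stage 4 is not the largest QIV-HD exposure step: by stage the QIV-HD totals in Table 5.1 are 150, 90, 105 and 90. Nor is giving 60 µg to this age group itself a departure from the design. Review of 60 µg in older children and of 45 µg in the same age group comes first, which fits the planned age de-escalation and dose ascension.

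**What to change.** Amend Protocol 5.1.1, 5.1.3 (Review of safety data), 5.1.6 and 12.4, and SAP 5.4 and 5.6, with matching edits where the Synopsis and SAP 3.1 and 3.2 repeat them. Suggested text:

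*If 60 µg is used in Stage 4, the SMT will review blinded D0 to D7 data once the first 60 subjects across Groups 6, 7 and 8 have V02 data. The two criteria of Section 5.1.6 apply. Enrollment continues during the review. If a criterion is met, the SMT decides whether further enrollment and pending second doses proceed. Second doses are not held automatically.*

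Counting all three groups brings in Group 8, the youngest. Leaving out an automatic hold respects Section 5.1.6, under which second doses go ahead as scheduled, and avoids pushing children, including those on licensed controls, outside the +7-day V03 window.

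The cost is one amendment, the SAP edit, one more SMT review and a false-trigger chance of about 0.01 (5% versus 3%). No extra subjects, visits or data are needed, because V02 staff already have the instruction "Record the D0 to D7 safety data in the CRB". No calendar time is lost unless a criterion is met.
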